9.6 Data Analyses

Data Analysis: To examine our aims and hypotheses we will utilize the generalized linear model, which allows specification of an appropriate distribution for each outcome that can accommodate continuous outcomes (e.g., normal distribution with identity or log link for self-reported disability) and presence/absence outcomes (e.g., binomial with logit link for probability of daily opioid use). We will not stratify our analyses by PTSD or depression, but will account for these variables in our data analysis. Furthermore, we will attend to the influence of missing data on our analyses, and plan on conducting missing values analysis to inform several sensitivity analyses (e.g., LOCF, multiple imputation, etc.) to ensure an intent-to treat principle is observed. Specifically, we will examine the MAR assumption by examining patterns of missingness conditional on baseline assessments, treatment adherence, or other time-varying predictors. Our RCT has one primary endpoint (Oswestry), so both primary and secondary outcomes will be interpreted at a conventional level of statistical significance, $p < 0.05$. To adhere to NIH policy of examining gender and ethnic subgroup analyses, we will add interaction terms (i.e., treatment group x subgroup) for each of our planned analyses. Each analysis is further detailed below:

AIM 1: Assess the efficacy of the FORT-A Program for improved pain management outcomes in (N=130) polymorbid OEF/OIF/OND PRC Veterans with chronic orthopedic pain using a 1:1 randomized clinical trial comparing FORT-A to standard PRC care. To examine our primary hypothesis, we will compare the self-reported disability scores of the two groups at 12-month follow-up while controlling for baseline scores (i.e., an ANCOVA approach). A statistically significant main effect will be interpreted as the groups exhibiting differential change in regards disability. Secondary analyses will use growth curve modeling (mixed effects hierarchical regression with polynomial change parameters) which will model differences in change trajectory over time between the groups across assessment occasions.

AIM 2: Assess the efficacy of FORT-A for decreasing the rate of opioid medication recidivism compared to standard PRC care in a sample of OEF/OIF/OND polymorbid LBP Veterans. To examine our primary hypothesis, we will compare the rate of opioid medication recidivism between the two groups monthly from baseline to 12-month follow-up. As noted above, 30-40% of TAU participants are expected to meet criteria for opioid recidivism (use of any opioid medication for 3 days or more in the last 30 days at each assessment). A statistically significant main effect will be interpreted as the groups exhibiting differential change in regards disability. Secondary analyses will be conducted using growth curve modeling (i.e., mixed effects hierarchical regression with polynomial change parameters to model differences in the trajectory of opioid use over time between the groups by time).

EXPLORATORY AIM 3: To examine the role of helplessness and perceived burdensomeness in predicting the trajectory of change over time, we will use latent

growth curve modeling. We will first model the trajectory of change in the two primary outcomes as a function of group (Aim 1 and Aim 2). We will then model the trajectories of helplessness and perceived burdensomeness as a function of group. Assuming both associations are observed (i.e., that group status is related to changes in the outcomes and the mediators), we will conduct hierarchical entry of group status and each mediator to examine if group status is still associated with outcome after adjusting for changes in the mediators. This will allow us to assess the role of the mediators in predicting the outcome and the proportion of change trajectory attributed to changes in these mediators.

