6.2.5 Completion/Final Evaluation

List each assessment to be performed at the participant's final visit.

Visit 16 (One-Year Follow-Up)	Psychosocial Assessment Pain Diary FCE Upload Actiwatch Upload MEMS Adverse Events Opioid/Medication Assessment (including CPRS and PAT) MQS STRONG STAR Common Data	± 50 weeks after treatment ± 2 weeks
----------------------------------	---	---

	Elements Exit Interview	
--	----------------------------	--

All participants will be asked to complete all final assessments, regardless of whether or not they complete the study. After completing the intervention, we will maintain monthly telephone contact with all participants to promote adherence to follow-up assessments and to give them an opportunity to report any adverse events they may have experienced since finishing the three-week intervention phase. This monthly contacts will also include monthly administration of the TLFB for pain medication and opioid medications and administration of the MQS. We will also use these monthly calls to identify and troubleshoot any potential problems with the Actiwatch or MEMS Caps.

Participants who were lost to contact at any point before the 12 month follow-up assessment will be contacted to complete the Missing Data Assessment, ODI, TLFB and Concomitant Meds Form. Participants will be mailed a letter explaining why they are being contacted, how long the phone interview will take, and what information we will collect. The letter will also include opt-out information. Within two weeks of the participants receiving this letter, we will contact participants to discuss whether they would like to participate. The Missing Data Assessment is a 4-item measure of global symptom improvement of pain, perception of satisfaction and burdensomeness of study treatments, and reason(s) for discontinuing study participation. This assessment will be used to assess missing data randomness and to categorize participants who discontinued study participation as a way to help impute missing data and improve future studies with these treatments in similar populations.

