We will enroll $n = 65$ ($N = 130$) and anticipate $\leq 30\%$ all-source attrition rate as in our previous study. Assuming that at the 12-month follow-up the standard care treatment arm will report mean (SD) ODI scores of 19.5 (6.6), using a two-tailed $\alpha = 0.05$, we will have power = 0.80 to detect effect sizes as small as $d = 0.50$. For the ODI, this is equivalent to a clinically meaningful 3.3 point difference between groups. In our original FORT trial, we observed a 9.2 point difference between individuals who were not lost to follow-up at 12-months. Thus, for the intention-to-treat analyses, where we expect that up to 30% of individuals will require imputation of some kind, our expected effect sizes can be attenuated by $\sim 60\%$ with sufficient power to detect a clinically meaningful difference. Differences smaller than 3.3 points on the ODI are unlikely to be clinically meaningful.

Treatment Assignment Procedures

Participants will be randomly assigned to each of the study arms based on the rationale and procedures outlined in sections 6.2.2 and 6.2.3 of this protocol. Masking will be managed using the diagram shown in Figure 2. Pursuant to this diagram, masking will be overseen and maintained through a collaboration between the study coordinator (who will not be blind to any part of this study to all for better tracking of participant flow and AEs; though the Coordinator will not take part in any evaluations and is forbidden to discuss blinded information with any study team member without first discussing it with the PI and the STRONG STAR Administrative Core) and the STRONG STAR Data Core (which maintains the link between identity and participant number). Masking of treatment arm to the participant or provider is absolutely impossible in a behavioral trial. Plans for

retention of the blind are described in sections 5.2, 5.4, and 6.2.3.1 of this protocol. If a blind must be broken (e.g, to protect the safety of a participant), then the blind can only be broken by the study Coordinator and/or Co-Coordinator after consultation and permission from the PI and the STRONG STAR Admin Core. To break the blind, the Coordinator will contact the STRONG STAR Data Core and request revelation of the participant identity and linked unique identifier.

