9.3 Definition of Populations

For this study, the per-protocol population will include all participants who completed all assessments and interventions with no major protocol deviations (as defined by Gupta, 2011). The primary analysis will be conducted on the Intent-to-Treat (ITT) population that will include all randomized participants who have completed baseline assessments. In the original trial, all FORT completers participated in all assessments, but approximately 20% of Treatment as Usual participants were lost to follow-up. Analysis of baseline data revealed that most missing data were missing at random.

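### The missingness check planned in Section 9.6 can contradict MCAR but can neither confirm nor refute MAR, and nothing else in the analysis plan covers outcome-dependent dropout

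*Combined protocol and SAP*

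**What the plan says.** Section 9.6 makes the primary analysis an ANCOVA of 12-month ODI on baseline. A missing-values analysis is to inform "several sensitivity analyses (e.g., LOCF, multiple imputation, etc.) to ensure an intent-to treat principle is observed". For the assumption itself the section says "we will examine the MAR assumption by examining patterns of missingness conditional on baseline assessments, treatment adherence, or other time-varying predictors". It gives no null hypothesis, test, threshold or decision rule, and it names no analysis designed for data missing not at random (MNAR).

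Section 9.3 reports that in the earlier trial all FORT completers took part in all assessments while about 20% of usual-care participants were lost. It adds: "Analysis of baseline data revealed that most missing data were missing at random".

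Section 6.2.5 and the last column of the Section 6.1 schedule provide for contacting participants who are lost or dropped. They are to give a four-item Missing Data Assessment, the ODI, the timeline followback and concomitant medications. Of the four-item form, 6.2.5 says "This assessment will be used to assess missing data randomness" and that it will help with imputation. Section 9.6 mentions neither the form nor the retrieved ODI.

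Section 9.2 expects that up to 30% of participants will need imputation.

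**The concern.** The step carries the label of one assumption and examines another. Relating missingness to baseline scores, adherence and time-varying measures asks whether dropout is unrelated to observed data, which is MCAR. A clear pattern could be read as MAR failing when an analysis conditioning on those variables is unbiased. A flat pattern could be read as support for MAR while dropout depends on the outcome. The sentence in 9.3 shows the second kind of inference already drawn from baseline data.

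The credibility of the 12-month ODI comparison is at stake. With up to 30% of scores missing, and with loss in the earlier trial reported on the usual-care side, outcome-dependent dropout in one arm is the case that matters for the treatment effect. The named sensitivity analyses do not address it directly. Standard multiple imputation assumes MAR, and LOCF is not built to represent a stated departure from it.

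**Working it through.** **1. The plan's own figure.** Section 9.2 gives 65 per arm, SD 6.6 and a two-sided 0.05 test, and says of d = 0.50 that "this is equivalent to a clinically meaningful 3.3 point difference between groups". Check: 3.3/6.6 = 0.50, and power = Φ(0.50 × √(65/2) − 1.960) = Φ(0.890) = 0.81, against the stated 0.80. The setting reproduces. The documents give no figure for the missingness check.

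**2. Definitions.** Let R = 1 if the 12-month ODI is observed, X the observed variables and Y the 12-month ODI.
- MCAR: P(R | X, Y) is constant.
- MAR: P(R | X, Y) = P(R | X), which may vary with X.
- MNAR: P(R | X, Y) still varies with Y, given X.

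The check looks at whether P(R | X) varies with X. If it does, MCAR is false, and MAR and MNAR both remain possible. If it does not, MCAR is possible and so is MNAR. Separating MAR from MNAR needs Y where R = 0, which the check does not have.

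**3. Simulation of one plausible version.** From the documents: N = 130, 1:1 allocation, 30% missing, effect 3.3 points, SD 6.6. Assumed: correlation of 12-month ODI with baseline 0.3, 0.5 or 0.7 (with 6-month ODI 0.5, 0.7 or 0.8), dropout odds ratio 2 or 3 per SD, normal outcomes, 6-month ODI fully observed, and a logistic likelihood-ratio test at 0.05. There were 1,500 trials per setting. Bias is that of the observed-case ANCOVA, towards zero.

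| Dropout depends on | Signal, baseline + arm | Signal, 6-month ODI added | Bias (points) |
|---|---|---|---|
| Nothing (MCAR) | 5-6% | 5-6% | about 0 |
| Baseline ODI (MAR) | 87-89% (OR 2), over 99% (OR 3) | 82-84% (OR 2), over 99% (OR 3) | about 0 |
| Part of ODI not predicted by baseline or arm, both arms | 4-6% | 20-69% | about 0 |
| Same, usual care only | 5-8% | 10-25% | 0.9-1.8 |
| Same, opposite directions by arm | 4-6% | about 5% | 1.8-3.3 |
| 12-month ODI itself, both arms | 14-86% | 29-94% | about 0 |

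In these settings the check signals most where the treatment comparison is unbiased and least where it is biased.

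**4. Usual-care dropout depending on 12-month ODI itself.** Assumed: 25% missing, baseline correlation 0.5, log-odds 0.4, 0.7 or 1.0 per SD. Baseline ODI alone signals in about 7%, 13% and 20% of trials. The 0.5 SD effect shrinks by about 0.08, 0.13 and 0.18 SD, which is × 6.6 = 0.5, 0.9 and 1.2 points. Adding 6-month ODI (correlation 0.7-0.8) with arm interactions raises detection to 11-12%, 21-32% and 41-48%. Imputing within arm from baseline and 6-month ODI cuts the shrinkage to about 0.06, 0.08 and 0.13 SD at correlation 0.7, or 0.03, 0.06 and 0.09 SD at 0.8. At 0.5 the gain is slight.

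**5. What a delta-adjusted analysis would ask.** If a fraction f of one arm is missing and its unseen scores differ from the MAR prediction by δ, that arm's mean moves by f × δ. With 30% missing, the 3.3-point effect reaches zero when unseen FORT-A scores are 3.3/0.30 = 11 points worse than predicted and usual care is unshifted. With 20% missing in usual care only, unseen scores there would have to be 3.3/0.20 = 16.5 points better than predicted. Statistical significance would be lost at smaller shifts.

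**The case against.** Section 9.6 states no null, alpha or rejection rule and makes no analysis conditional on a verdict. Looking at patterns of missingness to inform sensitivity analyses is ordinary practice for choosing imputation variables. The planned predictors go beyond baseline: ODI is also measured post-treatment and at 6 months, and adherence is included. Section 6.2.5 already collects information from lost participants to judge randomness and help imputation, in the same document. The sentence in 9.3 describes a trial whose analysis cannot be seen, and it governs nothing here. All of this stands, and it limits the point.

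Two stronger readings are tempting. A reader might infer that the check rejects whenever MAR is true and stays silent whenever dropout depends on the unseen ODI. It need not signal under MAR if dropout is also MCAR or only weakly related to the predictors. It is often not silent under MNAR, with signals in up to 94% of simulated trials when both arms drop out on ODI itself and 6-month ODI is included. A reader might also infer that a wrong verdict decides which analyses are run or reported. The text says only that the analysis informs them.

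The objection does not rescue the stated purpose. Richer predictors raise detection, but a signal still cannot separate MAR from MNAR. The data under 6.2.5 are collected but have no analysis in 9.6. They are also no clean test of MAR, because they come by telephone, from people who do not opt out, at the time of contact rather than necessarily at 12 months.

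**Conclusion.** The point holds as a mismatch between a planned analysis and its stated purpose. The step can show that data are not MCAR, but it cannot support or refute MAR. It will often signal when dropout depends only on observed variables and the adjusted analysis is unbiased. It can miss outcome-dependent dropout, above all when that is confined to one arm, runs in opposite directions by arm, or follows the part of ODI that the observed variables do not predict.

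In the simulated settings, the bias that can go unseen is about 0.5 to 1.8 of the planned 3.3 points with usual-care-only dropout, and 1.8 to 3.3 points with opposite directions. These figures are illustrative. They depend on the assumed correlations, dropout strength and choice of predictors, and they apply to the observed-case ANCOVA; multiple imputation with a strongly correlated 6-month ODI reduces them. That the check cannot identify MAR follows from the definitions and needs none of these assumptions. The primary ANCOVA itself is not at fault. The change should be made, and it is inexpensive.

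**What to change.** In Section 9.6:
- Describe the step as identifying predictors of dropout. Enter those variables in the imputation or likelihood model whatever their p-values.
- State MAR as an assumption that the observed data cannot verify.
- Link the Missing Data Assessment and the retrieved ODI (Section 6.2.5) to the analysis. Report, by arm, the mean difference with 95% interval between retrieved ODI and the MAR-model prediction matched to the time of contact. Call it partial evidence, for the reasons of mode, self-selection and timing given above.
- Use those differences to set the range of a simple delta-adjusted sensitivity analysis of the 12-month ODI, with shifts allowed to differ by arm.

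Do not rely on the statement in Section 9.3 that baseline data showed MAR.

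The cost is some SAP wording, one table and one sensitivity analysis, all from data already planned. The intervals will be wide. Taking SD 6.6 as a cautious value and assuming 5, 10 or 19 retrieved scores in an arm (30% of 65 is 19.5), the half-width is 1.96 × 6.6/√n = 5.8, 4.1 or 3.0 points. The comparison can therefore guide the choice of delta but cannot settle whether MAR holds.
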